### 8.3.2 DEFINITION OF SERIOUS ADVERSE EVENTS (SAE)

An adverse event (AE) is considered "serious" if, in the view of the sponsor-investigator, it results in any of the following outcomes: death, a life-threatening adverse event, inpatient hospitalization or prolongation of an existing hospitalization, a persistent or significant incapacity or substantial disruption of the ability to conduct normal life functions, or a congenital anomaly/birth defect. Important medical events that may not result in death, be life-threatening, or require hospitalization may be considered serious when, based upon appropriate medical judgment, they may jeopardize the participant and may require medical or surgical intervention to prevent one of the outcomes listed in this definition. Examples of such medical events include allergic bronchospasm requiring intensive treatment in an emergency room or at home.

### 8.3.3 CLASSIFICATION OF AN ADVERSE EVENT

### 8.3.3.1 SEVERITY OF EVENT

All AEs will be assessed by the investigator using a protocol defined grading system. AEs captured on the Total Safety Score worksheet will not be reported separately as adverse events but will be graded according to the scoring system associated with that tool, as appropriate for a study endpoint. For adverse events (AEs) not included in the protocol defined grading system or AEI list, the following guidelines will be used to describe severity.

- **Mild** – Events require minimal or no treatment and do not interfere with the participant’s daily activities.
- **Moderate** – Events result in a low level of inconvenience or concern with the therapeutic measures. Moderate events may cause some interference with functioning.
- **Severe** – Events that interrupt a participant’s usual daily activity and may require systemic drug therapy or other treatment. Severe events are usually potentially life-threatening or incapacitating. Of note, the term “severe” does not necessarily equate to “serious”.

### 8.3.3.2 RELATIONSHIP TO STUDY INTERVENTION

All adverse events (AEs) must have their relationship to study intervention assessed by the clinician who examines and evaluates the participant based on temporal relationship and his/her clinical judgment. The degree of certainty about causality will be graded using the categories below. In a clinical trial, the study product must always be suspect.

- **Related** – The AE is known to occur with the study intervention, there is a reasonable possibility that the study intervention caused the AE, or there is a temporal relationship between the study intervention and event. Reasonable possibility means that there is evidence to suggest a causal relationship between the study intervention and the AE.
- **Not Related** – There is not a reasonable possibility that the administration of the study intervention caused the event, there is no temporal relationship between the study intervention and event onset, or an alternate etiology has been established.

### 8.3.3.3 EXPECTEDNESS

The investigator will be responsible for determining whether an adverse event (AE) is expected or unexpected. An adverse event or suspected adverse reaction is considered “unexpected” if it is not listed in the approved product label attached in Appendix 1 or is not otherwise consistent with the risk information described in Section 2.3 of the study protocol.

## 8.3.4 TIME PERIOD AND FREQUENCY FOR EVENT ASSESSMENT AND FOLLOW-UP

The occurrence of an adverse event (AE) or serious adverse event (SAE) may come to the attention of study personnel during study visits and interviews, or other contacts with a study participant during the treatment and follow-up period.

All AEs will be captured on the appropriate case report form (CRF). Information to be collected includes event description, date of onset, clinician’s assessment of severity, relationship to study product as assessed by the investigator, and date of resolution/stabilization of the event. All AEs occurring while on study must be documented appropriately, according to the definitions in Section 8, regardless of

relationship. All AEs will be followed to adequate resolution or the end-of-the study. Local and systemic reactions during the 60-minute observation period will be captured on the Total Safety Score report form which includes specific criteria for assessing and grading adverse reactions to AIT. For patients experiencing a reaction, the observation period will be extended until the patient is stable. In accordance with Section 2.1, after each treatment visit, patients are counseled on how to recognize the signs of delayed-onset reactions, including worsening pain, tenderness, redness, swelling at the injection site and to assess the injection site for these symptoms for seven (7) following treatment. If they recognize these or other symptoms of a delayed-onset reaction, they are instructed to report these symptoms by phone.

Any medical condition that is present at the time that the participant is screened will be considered as baseline and not reported as an AE. However, if the study participant's pre-existing condition deteriorates at any time during the study, it will be recorded as an AE.

Changes in the severity of an AE will be documented to allow an assessment of the duration of the event at each level of severity to be performed. AEs characterized as intermittent require documentation of onset and duration of each episode.

The investigator or designee will record all events, defined as serious, unexpected, and related adverse drug reactions with start dates occurring any time after the initiation of treatment until seven (7) days after the third treatment will be reported in accordance with the requirements of 21 CFR 312, if applicable, to the manufacturer using their post-marketing safety report system, and to the IRB as an Unanticipated Problem in accordance with Section 8.4. At each study visit, the investigator will inquire about the occurrence of AE/SAEs since the last visit. Unresolved adverse events will be followed for outcome information until the end of the study.

---

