### **Local Reactions**

With diagnostic allergy testing, a positive skin reaction is to be expected in sensitive patients as part of the confirmatory diagnostic process. The positive reaction typically defined as an urticarial wheal with surrounding erythema (resembling somewhat a mosquito bite reaction) larger than the control site. The smallest reaction considered positive is erythema with a central papule at least 5 mm in diameter. In some cases, with no reaction at the control site, erythema can be considered an indication of sensitivity. In general, the size of wheal and erythema response correlates directly with the patient's sensitivity to the allergen. This study will employ histamine as a positive control. Thus, participants in this study can expect to experience at least one urticarial wheal associated with the allergy diagnosis.

For patients receiving AIT injection, some erythema, swelling or pruritus at the site of injection are common, the extent varying with the patient. Such reactions should not be considered significant unless they persist for at least 24 hours. Injections with allergenic extracts in 50% glycerin are known to cause discomfort at the site of the injection.

Local reactions (erythema or swelling) which exceed 4-5 cm in diameter are not only uncomfortable, but also indicate the possibility of a systemic reaction, especially if the dosage is increased. Large, persistent local reactions may be treated by local cold, wet dressings and/or the use of oral antihistamines. They should be considered a warning of possible severe systemic reactions and an indication of the need for temporarily reduced dosages. A mild burning immediately after the injection is to be expected. This usually subsides in 10 to 20 seconds.

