## 8.3 ADVERSE EVENTS AND SERIOUS ADVERSE EVENTS

### 8.3.1 DEFINITION OF ADVERSE EVENTS (AE)

Any untoward medical occurrence in a clinical investigation subject administered immunotherapy or matched placebo which does not necessarily have a causal relationship with the treatment and is not otherwise related to their underlying medical condition or a comorbid condition present at the time of enrollment. An AE can therefore be any unfavorable and unintended sign, symptom, or disease temporally associated with the use of the immunotherapy or other medicinal product, whether or not related to the medicinal product, that has an onset after enrollment in the study and the initiation of treatment, defined as the injection of study treatment and the seven day period following. Events reported via the patient diary on the daily symptom score are by definition symptoms of the underlying disease and are therefore not adverse events. Symptoms may fluctuate and thus changes in symptoms are not considered adverse events but are rather measures of treatment efficacy for the underlying condition. Pre-planned procedures are not considered adverse events. Pre-existing conditions, unless worsened are not considered adverse events. Whenever possible, adverse events will be consolidated into the underlying diagnosis rather than a collection of separately reported symptoms, as determined by the investigator.

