### 8.3.8 EVENTS OF SPECIAL INTEREST

Adverse Events of Interest (AEIs) include symptoms associated with local and systemic allergic reactions to AIT, up to and including anaphylaxis. Such events will be evaluated on the TSS worksheet rather than reported on separate AE or SAE forms. Specific AEIs associated with AIT include: Confusion, hypotension/collapse, unconsciousness, bradycardia, pallor, and urinary or fecal incontinence, which will be used to define severe reactions on the TSS worksheet. Diaphoresis, vomiting, presyncope, dyspnea, stridor, wheeze, chest/throat tightness or laryngeal edema, nausea, vomiting, and abdominal pain will define moderate reactions and reactions limited to the skin, including urticaria, erythema, injection site pruritis and angioedema will be defined as mild.

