10. SAFETY ANALYSIS

Safety analyses will compare treatment groups using appropriate methods according to their nominal or quantitative nature and will include descriptive statistics rather than formal hypothesis testing for noninferiority due to the small overall sample size. The study included a formal stopping rule in the event two systemic allergic reactions were detected.

The total safety score (TSS) and proportion of subjects with any treatment-emergent SAE, as defined in the composite safety endpoint, will be assessed using the Mann-Whitney test. Data will be presented in the form of descriptive statistics and appropriate tables and graphs with a conclusion on whether the significance level allowed the null hypothesis for each test to be rejected.

Safety Objective: To evaluate the safety profile of ILIT versus placebo using a standardized scoring system, the Total Safety Score worksheet, for AEs of interest (AEIs) up to 60 minutes post-procedure.

Statistical Analysis Plan

Safety Endpoints:

- Proportion of subjects experiencing a serious, treatment-emergent AE up to 60 minutes after an intranodal injection procedure
- Proportion of subjects experiencing systemic reactions to ILIT relative to placebo and severity of reactions relative to placebo as assessed by the Total Safety Score (TSS)
- Proportion of subjects reporting local injection site reactions relative to placebo and severity of local reactions relative to placebo, as assessed by the TSS

Additional safety tables and listings will include summaries of all patients experiencing anaphylaxis or treated with epinephrine, by group and a table of TSS reactions by severity by group.

Safety Population:

Safety analysis will include all participants who received at least one dose of study intervention regardless of whether they provided any diary data.

Calculation cumulative safety score (sum of TSS) across all patients by group will be performed in accordance with the scoring instruction described in section 7.4

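### Allergic reactions that first appear or worsen after the patient leaves observation are not counted in safety endpoints 2 and 3, and the protocol's rules on where to record them conflict

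*Protocol*

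**What the plan says.** The TSS worksheet (protocol Appendix 3, repeated in SAP 7.4) marks local and systemic reactions by severity and gives each injection one score from 0 to 4. Safety endpoints 2 and 3 rest on it. Endpoint 3 in SAP section 10 reads "Proportion of subjects reporting local injection site reactions relative to placebo and severity of local reactions relative to placebo, as assessed by the TSS". Neither endpoint carries a time window, whereas endpoint 1 names 60 minutes. The window for the TSS comes from its objective (protocol section 3, SAP section 10), which is limited to 60 minutes, and from protocol 8.3.4: "Local and systemic reactions during the 60-minute observation period will be captured on the Total Safety Score report form". The same section adds "For patients experiencing a reaction, the observation period will be extended until the patient is stable".

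The rules on which form to use are:

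- Protocol 8.3.8, on allergic reactions to immunotherapy: "Such events will be evaluated on the TSS worksheet rather than reported on separate AE or SAE forms". It has no time limit.
- Protocol 8.3.3.1: "AEs captured on the Total Safety Score worksheet will not be reported separately as adverse events". This covers only what the worksheet has already captured.
- Protocol 8.3.4 sends every adverse event to a case report form. Protocol 8.3.1 sets the onset period for adverse events, "defined as the injection of study treatment and the seven day period following".

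The protocol expects late reactions. Under 8.3.4, patients are counselled to check the injection site for seven days and to telephone if symptoms appear. No form is named for these calls. On local reactions, section 2.3.1 says "Such reactions should not be considered significant unless they persist for at least 24 hours". SAP 10.2 tabulates spontaneously reported adverse events by body system and treatment group.

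**The concern.** Safety is the primary objective, and endpoints 2 and 3 are where the two arms are compared on local and systemic reactions. A form completed while the patient is under observation can count a local reaction that fades within the hour. It cannot show whether a reaction lasted a day, which is the persistence that section 2.3.1 ties to significance. Reactions that begin at home are ones the protocol asks patients to look for, yet no endpoint picks them up.

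The conflict between the form rules adds a second risk. A site that applies 8.3.8 literally and also applies the observation-period limit of 8.3.4 could enter a delayed reaction on neither form. Another site or coordinator, relying on 8.3.3.1, would enter it as an adverse event. The safety tables would then depend partly on how the rules were read.

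**Working it through.** The plan states no figure on this point, so there is nothing to reproduce. The check applies the rules to four invented records.

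| Record | 8.3.4 | 8.3.8 | 8.3.3.1 | Endpoints 2 and 3 |
|---|---|---|---|---|
| Redness at 20 minutes, gone by 50 | Worksheet | Worksheet, not AE form | Captured, so no separate report | Endpoint 3, score 1 |
| Node swelling from that evening to day 3, phoned in | After the worksheet period; a CRF if it is an AE | Worksheet, not AE form | Not captured, so AE report is open | No rule counts it |
| Hives at home at 3 hours | As above | As above | As above | No rule counts it |
| Redness seen in clinic, worse at home next day | Clinic part on worksheet; severity change to be documented, form not named | Worksheet, not AE form | Captured, so no separate report | Clinic state only |

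Rows 2 to 4 show the conflict. In rows 2 and 3, 8.3.8 and 8.3.3.1 point to different forms. In row 4, both point away from the AE form, while 8.3.4 still wants the change in severity documented.

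**If every late reaction does reach the AE form.** It is tabulated under SAP 10.2. No rule applies the TSS key to it or adds it to endpoints 2 or 3. SAP 7.4 scores the TSS at Treatment Visits 1, 2 and 3 only, and the schedule of events agrees.

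**Can 24-hour persistence be recovered?** The worksheet has no field for onset time or duration. Section 8.3.4 asks for dates of onset and resolution, and for enough detail to assess duration at each severity level, but lists no clock time. From dates alone:

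- same date: less than 24 hours;
- consecutive dates: anything above 0 and below 48 hours, so undecided;
- resolution two or more dates after onset: more than 24 hours.

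Dates therefore settle some cases and leave the overnight reaction open.

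**Size per participant.** With 32 enrolled 1:1, n = 32/2 = 16 per arm. If k participants in an arm have only a late reaction of the relevant type, that arm's reported proportion is lower by k/16:

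- k = 1: 1/16 = 6.25 points
- k = 2: 2/16 = 12.5 points
- k = 3: 3/16 = 18.75 points

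With the 23 participants of the sample size section, split 12 and 11, one participant is 1/12 = 8.3 or 1/11 = 9.1 points. The documents give no value for k in either arm.

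**The case against.** The strongest reply is that late reactions are not lost. The AE period runs seven days past injection, all AEs go on a case report form, AEs since the last visit are asked about at each visit, and SAP 10.2 reports them by arm. Section 8.3.3.1 stops separate reporting only of what the worksheet already holds. This stands. A reader might infer that delayed reactions are barred from both forms and scored as zero, but that needs 8.3.8 to be read without a time limit for the AE form and with one for the worksheet. The text is in conflict; it does not lay down that rule.

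Second, the worksheet's own instruction refers to reactions following injection, without a limit, and endpoints 2 and 3 state no window. A site could in principle reopen the worksheet. That is possible, but nothing provides for it, and the TSS objective and the visit-based scoring in SAP 7.4 point the other way.

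Third, a reader might think that a reaction getting worse in the clinic after the first hour is missed. The documents do not support that. Observation is extended after a reaction, the worksheet scores the most severe reaction, and the SAP's summary of patients given epinephrine has no time limit. Only worsening after the patient leaves is affected.

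Fourth, 60 minutes is a prespecified, staff-observed window, longer than the 30 minutes in the label, and section 2.3.1 says few severe systemic reactions were reported after an hour. This supports keeping the window as the main result. It also suggests that the gap concerns local and milder reactions more than severe ones. Section 2.3.1 does not rest on persistence alone either: it also treats local reactions above 4-5 cm as a warning.

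**Conclusion.** The point holds in a limited form. As the plan is written, endpoints 2 and 3 describe what staff see during the observation period. Reactions that start or worsen after the patient leaves fall outside them, the form for such reactions is contradictory, and at best they appear ungraded by the TSS key in a general AE table. That they are left out is an inference from the TSS objective, 8.3.4 and SAP 7.4, because the endpoints name no window.

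The total size cannot be given. A reader might try to derive it from the 83% with local discomfort or node swelling in an earlier intralymphatic trial (protocol 2.2). That figure pools a six-injection and a three-injection arm, includes discomfort, which is not a listed worksheet item, and says nothing about onset, so any late share would be invented. A reader might also infer that the gap makes active treatment look closer to placebo. No passage says that late reactions are more frequent in one arm than in the other, so the direction is open. What can be said is that arms this small move by 6 to 9 percentage points per participant, so a few late reactors would be visible in the result.

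**What to change.** 1. Reconcile protocol 8.3.3.1, 8.3.4 and 8.3.8. The worksheet covers the observation period, including its extension after a reaction. Any local or systemic allergic reaction with onset or worsening after that goes on the AE/SAE form, with onset time and duration, and is graded with the TSS key.
2. State the 60-minute window in the wording of endpoints 2 and 3, and say how reactions in the extended observation are handled.
3. In SAP section 10, report beside the 60-minute result a supplementary proportion per arm through day 7 after each injection, with local reactions lasting at least 24 hours as a separate row.

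If injections are finished when this is taken up, existing AE pages and call notes can be classified before unblinding, with missing onset times shown as unknown.

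The cost is a few sentences in each document, two fields on the AE form and an added column and row in one table. The calls and AE reviews are already planned. The downside is that late events are self-reported. After the third injection, the next scheduled AE review is the end-of-study visit after the pollen season, so timely capture then depends on the telephone call. For that reason the day-7 result should stand beside the 60-minute result and not replace it.

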### 8.3.5 ADVERSE EVENT REPORTING

Adverse events will be analyzed and reported in a peer-reviewed publication following the completion of this study and tabulated and reported in Clinicaltrials.gov if 42 CFR 11 is applicable and this study is conducted under an IND.

---

### 8.3.6 SERIOUS ADVERSE EVENT REPORTING

The investigator will report to the IRB any serious adverse event (SAE) that meets the IRB's definition of an Unanticipated Problem (UP) in accordance with the IRB's reporting procedures for Unanticipated Problems, as described in Section 8.4. Serious, unexpected, and related adverse drug reactions will be reported under the requirements of 21 CFR 312, as applicable.

All SAEs will be followed until satisfactory resolution or until the investigator deems the event to be chronic or the participant is stable. Other supporting documentation of the event will be made available to the IRB and FDA upon request.

---

### 8.3.7 REPORTING EVENTS TO PARTICIPANTS

In the event that the IRB determines that the risk-to-benefit ratio of the study has changed or additional information, as determined by the sponsor-investigator or IRB, has emerged during the course of the study, including information developed during the study as part of this research, or other information in published literature reports of ILIT, the ICF will be revised and an updated ICF will be provided to study participants for review and discussion to determine whether they wish to continue their participation in

the study. Should they agree to continue participation, subjects will sign the revised informed consent and their agreement will be noted in their medical record.

### 8.3.8 EVENTS OF SPECIAL INTEREST

Adverse Events of Interest (AEIs) include symptoms associated with local and systemic allergic reactions to AIT, up to and including anaphylaxis. Such events will be evaluated on the TSS worksheet rather than reported on separate AE or SAE forms. Specific AEIs associated with AIT include: Confusion, hypotension/collapse, unconsciousness, bradycardia, pallor, and urinary or fecal incontinence, which will be used to define severe reactions on the TSS worksheet. Diaphoresis, vomiting, presyncope, dyspnea, stridor, wheeze, chest/throat tightness or laryngeal edema, nausea, vomiting, and abdominal pain will define moderate reactions and reactions limited to the skin, including urticaria, erythema, injection site pruritis and angioedema will be defined as mild.

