**3 OBJECTIVES AND ENDPOINTS**

OBJECTIVES	ENDPOINT(S)	JUSTIFICATION FOR ENDPOINT
Primary		

To evaluate the safety of ILIT for Mountain Cedar pollinosis relative to placebo control based on the proportion of subjects receiving allergenic extract versus the proportion of subjects receiving placebo that:
 
 
1. experience anaphylaxis, or
 
2. are treated with epinephrine, or
 
3. experience any other treatment-emergent, serious adverse event (SAE) within 60 minutes of the ILIT procedure.
 
	
 
1. Relative proportion of subjects experiencing a serious, treatment-emergent AE up to 60 minutes after the ILIT procedure.
 
	
Risk of anaphylactic reactions is inherent in AIT and dose adjustments are required to continue therapy. This study will evaluate the frequency of these and related serious, treatment-emergent reactions to understand whether the individualized starting dose yields a safety profile for ILIT treatment of mountain cedar allergy that is consistent with other immunotherapies. Rates of anaphylactic reactions following in studies of SCIT and SLIT have been reported at about 1% of patients, which is similar to the frequency across all previous studies of ILIT.

Secondary		

 
1. To evaluate the efficacy of ILIT relative to placebo during the 2018-2019 Texas Mountain Cedar allergy season using total combined score (TCS), a composite of the daily symptoms score (DSS) and daily medication score (DMS).
 
	
 
1. Difference in reported average daily total combined score (TCS) between ILIT and placebo groups during the 2018-2019 Mountain Cedar pollen season. Relative number of days during the allergy season that TCS is lower in the ILIT group relative to the placebo group.
 
	
The European Academy of Allergy and Clinical Immunology (EAACI; Pfaar et al., 2014) recommends the TCS, a composite of daily symptom score (DSS) and daily medication score (DMS) as the standard primary endpoint for randomized controlled trials in AIT for allergic rhinoconjunctivitis. This endpoint has been used in previous pivotal trials of AIT (for an example see Blaiss et al. 2010).

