**14 APPENDIX 3 ASSESSMENT TOOLS AND RATING SCALES**

**Total Safety Score (TSS) Worksheet**

Subject ID:

Injection # (write in 1, 2, or 3):

RECORDING INSTRUCTIONS: Mark/code the box(es) indicating reactions experienced by this subject following injection (D = definitely related to study, P = probably related to study, N = not related to study)

ILIT protocol defined grading scale for severity# of adverse events			
	Mild	Moderate	Severe
LOCAL REACTIONS			
Lymph node swelling			
Itch			
Redness			
Other*			
SYSTEMIC REACTIONS			
Rhinorrhea			
Sneezing			
Dyspnea			
Cough			
Wheeze			
Pruritus			
Rash			
Angioedema			
Nausea			
Vomiting			
Diarrhea			
Headache			
Other*			

SCORING INSTUCTIONS: Give one score for most severe reaction (see scoring key on back) - min score 0, max score 4

SCORE for this injection	
---------------------------------	--

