2.3 Study Endpoints

The endpoints defined for this study are as follows:

Primary Efficacy Endpoint:

1. Average daily TCS during the 2018-2019 Mountain Cedar pollen season

Secondary Efficacy Endpoints:

Statistical Analysis Plan

1. Proportion of days during pollen season for which active patients experience a lower TCS than placebo patients
2. Patient reported pain or discomfort immediately after and 30 minutes post ILIT procedure
3. Patient-reported treatment satisfaction at the end of the study
4. Reduction in skin reactivity assessed using allergenic-specific serum IgE testing from pre-treatment to post-treatment (the end-of-study visit)

Exploratory Endpoints:

1. Use of rescue inhalers by patients with stable asthma

Safety Endpoints:

1. Proportion of subjects experiencing a serious, treatment-emergent AE up to 60 minutes after an intranodal injection procedure
2. Proportion of subjects experiencing systemic reactions to ILIT relative to placebo and severity of reactions relative to placebo as assessed by the Total Safety Score (TSS)
3. Proportion of subjects reporting local injection site reactions relative to placebo and severity of local reactions relative to placebo, as assessed by the TSS

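### The primary safety objective is a three-part composite, but every endpoint list counts only serious AEs, and the worksheet that records allergic reactions captures neither seriousness nor anaphylaxis

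*Protocol*

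**What the plan says.** **Objective.** Protocol 1.1, Protocol 3 and SAP 2.1 give the primary safety objective three alternatives: anaphylaxis, treatment with epinephrine, or a third that reads in Protocol 3 as "experience any other treatment-emergent, serious adverse event (SAE) within 60 minutes of the ILIT procedure". Protocol 6.5.1 calls epinephrine use a component of the primary safety outcome. Protocol 9.4.4 and SAP 10 refer to a composite safety endpoint.

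**Endpoint.** Protocol 3 defines it as "Relative proportion of subjects experiencing a serious, treatment-emergent AE up to 60 minutes after the ILIT procedure". SAP 2.3 has "Proportion of subjects experiencing a serious, treatment-emergent AE up to 60 minutes after an intranodal injection procedure", and SAP 10 repeats it. The lists in Protocol 1.1 and 9.1 are to the same effect. None names anaphylaxis or epinephrine. SAP 1 states that SAP definitions take precedence for analysis.

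**Capture.** Protocol 8.3.8 defines the adverse events of interest as "symptoms associated with local and systemic allergic reactions to AIT, up to and including anaphylaxis" and continues: "Such events will be evaluated on the TSS worksheet rather than reported on separate AE or SAE forms". Protocol 8.3.3.1 says the same: "AEs captured on the Total Safety Score worksheet will not be reported separately as adverse events". Protocol 8.3.4 puts all AEs on the case report form, then assigns reactions in the 60-minute observation period to the TSS form.

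**Worksheet.** The instruction in Protocol Appendix 3 is "Mark/code the box(es) indicating reactions experienced by this subject following injection". Each mark carries a relatedness code and sits in a mild, moderate or severe column. Each injection then gets one score from 0 to 4.

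**The concern.** Protocol 3 justifies the primary safety endpoint by the risk of anaphylaxis. In the hour after an injection, the serious events to be expected are mainly allergic reactions. Those are the events that 8.3.8 and 8.3.3.1 keep off the AE and SAE forms, while the endpoint as listed counts serious AEs. If the endpoint is programmed from SAE records, the reactions it was written for may not reach it.

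Safety is the primary objective of this trial, and Protocol 9.4.2 places efficacy second to it. Two analysts following these documents could report different primary safety proportions from the same patients.

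**Working it through.** The documents state no figure for this endpoint, so there is nothing to reproduce. The check compares definitions and sources, then gives the scale.

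**1. Objective against endpoint.** The objective is met by any of three events. The listed endpoint is met by one, a serious AE. The seriousness criteria in Protocol 8.3.2 do not mention epinephrine, so a patient given epinephrine for a reaction not judged serious meets the objective but not the listed endpoint. The objective's third part speaks of any *other* SAE, which implies that anaphylaxis is itself serious; yet 8.3.8 keeps it off the SAE form. The analysis sentence in Protocol 9.4.4 and SAP 10 mentions a composite but tests the proportion with any treatment-emergent SAE, and neither endpoint list defines that composite.

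**2. Can the worksheet supply what is missing?**
- It has no seriousness item. Protocol 8.3.3.1 itself warns that severe and serious are different things, so a severe grade or a score of 4 cannot stand in for an SAE.
- It has no anaphylaxis row. Nor do the signs that 8.3.8 uses to define severe reactions (confusion, hypotension or collapse, unconsciousness, bradycardia, pallor, incontinence) have rows. They fit only under the free-text row for other reactions.
- No rule in either document turns a worksheet entry into an endpoint event.

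**3. Three cases within 60 minutes.**

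| Case | Meets the objective | Counted if the listed endpoint is derived from SAE records |
|---|---|---|
| Anaphylaxis, recorded on the worksheet only | Yes | No |
| Epinephrine given, reaction not judged serious | Yes | No |
| Serious event that is not an allergic reaction, on an SAE form | Yes | Yes |

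**4. Scale.** Inputs: up to 16 per group, and 23 subjects in total, or about 12 per group (Protocol 9.2); anaphylaxis in about 1% of patients (Protocol 3).
- One case: 1/16 = 6.3%; 1/12 = 8.3%.
- Expected anaphylaxis cases in an arm of 16 at 1%: 16 × 0.01 = 0.16.
- Chance of at least one, 1 − (1 − p)^n: at 1%, 1 − 0.99^16 = 14.9% and 1 − 0.99^12 = 11.4%. The rate with this extract by this route is unknown. At assumed rates of 5% and 10%, the chance with 16 patients is 56.0% and 81.5%.
- Exact 95% intervals: 0/16 gives 0 to 20.6%; 1/16 gives 0.2% to 30.2%.

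At the protocol's own rate the arm will most likely have no case or one, so whether one case counts can settle the reported proportion.

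**The case against.** The best defence is that the routing rule concerns paperwork, not classification. Seriousness under 8.3.2 depends on outcome, whichever form is used. Protocol 8.2 names the TSS as one of the means by which AEs and SAEs are collected, and Protocol 9.4.8 plans individual tables for serious events of interest, so the authors expected some worksheet events to be classed as serious. The sentence in 8.3.3.1 goes on to say that these events are graded on the tool's own scale for endpoint use, which reads like avoidance of duplicate entry. The composite is plain in the objective and is mentioned in Protocol 6.5.1, 9.4.4 and SAP 10. Epinephrine use has its own CRF record. SAP 10 adds summaries of patients with anaphylaxis or epinephrine and a table of TSS reactions by severity.

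Most of this stands. It shows that the intended endpoint is the composite and that the information is collected. It does not close the gap. The prevailing SAP endpoint text is still the serious-AE wording, and SAP 10 presents its anaphylaxis and epinephrine summaries as additional to the endpoints. If worksheet events are to be classed as serious, the documents name no field in which that judgement is recorded. Anaphylaxis is the most exposed part, since it has neither an operational definition nor a source field.

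**Conclusion.** The concern holds as a mismatch between objective, endpoint wording and data source. An endpoint derived as written from SAE records can omit an anaphylaxis or epinephrine case. One omitted case moves an arm of 16 from 6.3% to 0%, or an arm of 12 from 8.3% to 0%. This assumes that the programmer follows the SAP endpoint text and uses SAE forms as the source; a programmer who follows the objective would count the case. The roughly 15% chance of any anaphylaxis in 16 patients rests on the protocol's 1%, which Protocol 3 takes from other immunotherapy routes and calls similar to earlier intralymphatic studies.

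A reader might infer three stronger things that the documents do not support.
- *That the reactions are lost.* They are on the worksheet, epinephrine is in the CRF, and SAP 10 tabulates both.
- *That they escape the study hold.* One trigger in Protocol 8.2 depends on an SAE, but another reads grade 3 systemic reactions directly from the worksheet.
- *That they escape reporting under Protocol 8.3.6.* That section depends on the nature of the event (an unanticipated problem, or serious, unexpected and related), not on whether an SAE form exists.

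**What to change.** 1. In the endpoint lists of Protocol 1.1, 3 and 9.1 and of SAP 2.3 and 10, define the primary safety endpoint as the proportion of subjects with any of anaphylaxis, treatment with epinephrine, or any other treatment-emergent SAE. State the 60-minute window for each part; as laid out, the objective attaches it only to the third.
2. In the SAP derivations, name the source for each part: the TSS worksheet for anaphylaxis, with the definition to be applied; the epinephrine CRF record; and the SAE form.
3. Amend Protocol 8.3.8 and 8.3.3.1 so that a worksheet reaction meeting the 8.3.2 criteria is also entered on the SAE form. Alternatively, add seriousness and anaphylaxis fields to the worksheet. If the first option is chosen, anaphylaxis still needs an identifiable field.
4. Reconcile 8.3.8 and 8.3.3.1 with 8.3.4, for example by stating that the TSS form is part of the case report form.

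The cost is a few sentences in each document, one derivation in the SAP, and slight double entry for rare events. No new assessment of patients is needed.
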